6.1.1. Part 1 Halting Rules

- 1. Any participant experiences a vaccine-related SAE.
- 2. Two or more participants experience the same or similar Grade ≥3 solicited AE (first and second vaccinations to be assessed separately).
- 3. Two or more participants experience the same or similar Grade ≥3 unsolicited single AE preferred term or clinical laboratory AE which the investigator assesses as possibly, probably or definitely related to study vaccine.
- 4. Occurrence of severe COVID-19 in any participant as defined below. If this halting rule is met, all available clinical, nonclinical safety and immunogenicity data will be reviewed by the IDMC to evaluate for potential vaccine enhanced COVID-19.

Per FDA's June 2020 Guidance Development and Licensure of Vaccines to Prevent COVID-19, severe COVID-19 disease is defined as virologically confirmed SARS-CoV-2 infection with any of the following:

- a. Clinical signs at rest indicative of severe systemic illness (respiratory rate ≥30 beats per minute, heart rate > 125 per minute, peripheral hemoglobin oxygen saturation [SpO₂] <93% on room air at sea level or partial pressure of oxygen [PaO₂]/fraction of inspired oxygen [FiO₂] < 300 mm Hg)
- Respiratory failure (defined as needing high-flow oxygen, noninvasive ventilation, mechanical ventilation or extracorporeal membrane oxygenation [ECMO])
- c. Evidence of shock (Systolic blood pressure < 90 mm Hg, diastolic blood pressure <60 mm Hg, or requiring vasopressors)
- d. Significant acute renal, hepatic, or neurologic dysfunction
- e. Admission to an intensive care unit (ICU)
- f. Death

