Moderate	 At least one or more of the following: Fever (defined by subjective or objective measure, regardless of use of anti-pyretic medications) + any 2 COVID-19 symptoms in Table 6 for ≥ 3 days (need not be contiguous days) High fever (≥ 38.4°C) for ≥ 3 days (need not be contiguous days) Any evidence of significant LRTI: Shortness of breath (or breathlessness or difficulty breathing) with or without exertion (greater than baseline) Tachypnea: 20 to 29 breaths per minute at rest SpO2: 94% to 95% on room air Abnormal chest x-ray or chest CT consistent with pneumonia or LRTI Adventitious sounds on lung auscultation (e.g., crackles/rales, wheeze, rhonchi, pleural rub, stridor)
Severe	 At least one or more of the following: Tachypnea: ≥ 30 breaths per minute at rest Resting heart rate ≥ 125 beats per minute SpO₂: ≤ 93% on room air or PAO₂/FiO₂ < 300 High flow oxygen therapy or NIV/NIPPV (e.g., CPAP or BiPAP) Mechanical ventilation or ECMO One or more major organ system dysfunction or failure (e.g., cardiac/circulatory, pulmonary, renal, hepatic, and/or neurological, to be defined by diagnostic testing/clinical syndrome/interventions), including any of the following: ARDS Acute renal failure Acute right or left heart failure Septic or cardiogenic shock (with shock defined as SBP < 90 mm Hg OR DBP < 60 mm Hg Acute stroke (ischemic or hemorrhagic)

Table 5Definitions of COVID-19 Severity

Abbreviations: AMI = acute myocardial infarction; ARDS = acute respiratory distress syndrome; BIPAP = bi-level positive airway pressure; CPAP = continuous positive air pressure; CT = computed tomography; DBP = diastolic blood pressure; DVT = deep vein thrombosis; ECMO = extracorporeal membrane oxygenation; FiO_2 = fraction of inspired oxygen; ICU = intensive care unit; LRTI = lower respiratory tract infection; NIV = non-invasive ventilation; NIPPV = non-invasive positive pressure ventilation; PAO₂ = partial pressure of oxygen in the alveolus; PE = pulmonary embolism; SBP = systolic blood pressure; SpO₂ = oxygen saturation.

Table 6Qualifying Symptoms of Suspected COVID-19

- Fever
- New onset cough
- New onset or worsening of shortness of breath or difficulty breathing compared to baseline
- New onset fatigue
- New onset generalised muscle or body aches
- New onset headache lasting \geq 48 hours
- New loss of taste or smell
- Acute onset of sore throat, congestion, and runny nose
- New onset nausea, vomiting, or diarrhea lasting \geq 48 hours

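### Halting rule 4 leaves out heart rate of exactly 125 and SpO2 of exactly 93%, both graded severe in Table 5: a minor inconsistency in a safety stop

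*Combined protocol and SAP*

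**What the plan says.** Section 6.1.1, rule 4, halts the study when any one Part 1 participant has severe COVID-19, and supplies its own definition. It attributes that definition to the FDA, citing the "June 2020 Guidance Development and Licensure of Vaccines to Prevent COVID-19, severe COVID-19 disease is defined as" confirmed infection plus any one of items a to f. Item a lists resting vital signs: "respiratory rate ≥30 beats per minute", "heart rate > 125 per minute", SpO2 "<93% on room air at sea level", or an oxygen ratio below 300. Item c covers shock: "Systolic blood pressure < 90 mm Hg, diastolic blood pressure <60 mm Hg", or a need for vasopressors. Item d covers renal, hepatic or neurologic dysfunction.

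The severity grades are in Section 7.1.1, in the table labelled Table 5 there (some other sections cite it as Table 6). Its severe grade includes "Resting heart rate ≥ 125 beats per minute" and SpO2 "≤ 93% on room air or" an oxygen ratio below 300. Its moderate grade has SpO2 of "94% to 95% on room air".

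Part 2 rule 4 (Section 6.1.2) reuses the Section 6.1.1 definition, but the halt there also needs an IDMC finding of vaccine-enhanced disease.

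**The concern.** The protocol defines severe COVID-19 twice, and the two definitions disagree at two readings. In both, the halting rule is the narrower one. No section explains the difference.

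Rule 4 is a single-case trigger intended to catch possible vaccine-enhanced disease early, so one participant decides whether dosing stops. The neighbouring safety provisions rely on Section 7.1.1: the risk table in Section 2.3.1 assesses severity for enhanced disease with that case definition, and Section 8.5.2 ties ad hoc IDMC meetings to COVID-19 as defined there. Only the automatic halt uses the other definition. A site could correctly grade a case severe and see no halt follow.

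**Working it through.** No sample size, power or alpha is involved, and there is no planned figure to reproduce. The check compares the two definitions line by line and then tests the boundary values.

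**Step 1. Numeric limits that appear in both places**

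| Sign | Section 6.1.1 | Table 5, severe | Agree? |
|---|---|---|---|
| Respiratory rate | ≥ 30 | ≥ 30 | yes |
| Heart rate | > 125 | ≥ 125 | no |
| SpO2, room air | < 93% | ≤ 93% | no |
| Oxygen ratio | < 300 | < 300 | yes |
| Systolic pressure | < 90 | < 90 | yes |
| Diastolic pressure | < 60 | < 60 | yes |

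Four of the six agree in value and sign, and two differ in sign only. Table 5 prints the oxygen ratio with the symbol for alveolar rather than arterial pressure; the comparison here is of the number and the sign.

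**Step 2. Values around each boundary, with no other criterion met**

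| Reading | Halt by 6.1.1? | Severe by Table 5? | Halt with ≥ 125 and ≤ 93%? |
|---|---|---|---|
| Heart rate 124 | no | no | no |
| Heart rate 125 | **no** | **yes** | yes |
| Heart rate 126 | yes | yes | yes |
| SpO2 92% | yes | yes | yes |
| SpO2 93% | **no** | **yes** | yes |
| SpO2 94% | no | no | no |

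The SpO2 rows assume a reading on room air at sea level. Table 5 bands saturation in whole percentages and its moderate band stops at 94%, so 93% is a complete reportable reading that can only be severe. Both sections refer to heart rate at rest, so posture or exertion does not explain the difference.

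**Step 3. Would the two sign changes align the halt with Table 5?** Not fully. Table 5 also counts cardiac or circulatory dysfunction, such as acute heart failure, as severe. Item d does not mention the heart, and item c reaches it only through shock. A case of acute heart failure without shock, and meeting no other item, would still be severe in Table 5 and outside rule 4.

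**Step 4. Other routes by which a boundary case could reach the IDMC**

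- A medically attended event goes to the sponsor within 24 hours (Section 7.3.1, Table 7).
- The Medical Monitor is to flag promptly any event that may count towards a halting rule, and may request an IDMC review that can suspend the study (Section 8.5.1).
- The IDMC may meet ad hoc over possible enhanced disease (Section 8.5.2).
- The IDMC reviews Part 1 safety data at set points before the next cohorts and before Part 2 (Sections 3.2.1 and 8.5.2).

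The first route only informs the sponsor, the next two depend on judgement, and the last is timed to cohort milestones. None stops dosing automatically.

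**The case against.** The strongest reply is that rule 4 carries its own definition, so a site can apply it without Table 5 and no operational ambiguity arises. The two lists also differ elsewhere: Section 6.1.1 names ICU admission, death and vasopressors, which Table 5 as printed does not. That makes the rule workable, but it does not make it consistent with the protocol's severity grade.

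A second reply is that the definition is credited to FDA guidance, which may itself use strict signs. A reader might go further and infer that the sponsor miscopied the guidance. The guidance is not among the documents, so they support neither reading. The direction of the change rests on Table 5 and on caution in a safety stop, not on the guidance.

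A third reply concerns consequence, and much of it stands. The routes in step 4 keep the case visible, and rule 1 halts on any vaccine-related SAE whatever the heart rate or saturation. Once Part 1 dosing is complete, a halt could only delay Part 2, which already needs an IDMC recommendation and FDA concurrence. The Version 5.0 change summary describes clarifications already issued to sites during Part 1, which suggests that little of Part 1 dosing may have remained. These points reduce the weight of the finding, but the mismatch remains and Part 2 reuses the definition.

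A reader might also infer a further gap from the sea-level wording, which appears only in Section 6.1.1. No site altitude is given and no consequence can be shown, so that is not part of this point.

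**Conclusion.** The inconsistency is real and minor. It affects exactly two readings, heart rate 125 and SpO2 93%, and only when no other Section 6.1.1 item is met. At those readings a case that the protocol grades severe does not trigger the automatic single-case halt in Part 1. The Part 2 effect is smaller because an IDMC finding of enhanced disease is required there anyway. No vaccine-efficacy analysis is touched.

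A reader might infer that severe cases could go unnoticed by the IDMC, or that the halting rule fails in general. The documents do not support either: four of the six shared limits agree, the rule works on either side of each boundary, and several reporting routes remain.

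The documents give no frequency for severe or boundary-value cases, so no probability is offered. That the event is likely rare is a judgement from about 72 Part 1 participants chosen to be at low risk of severe disease (Section 3.2). The conclusion assumes that the strict signs are as printed. The inclusive sign for respiratory rate in the same sentence makes that probable.

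**What to change.** In Section 6.1.1 item a, change the limits to heart rate ≥ 125 per minute and SpO2 ≤ 93%. Check the result against the FDA guidance cited there and, if it departs from that source, say so in the attribution. Part 2 rule 4 then follows without further edits.

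State whether the halt is meant to cover every case that Table 5 grades severe. If it is, add acute cardiac dysfunction to item d, because the sign changes alone do not achieve that. Keep the other items, including ICU admission and death. The altitude wording can stay as it is.

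The cost is one edited line, or two with the cardiac addition, and a source check. The downside is a possible extra pause for IDMC review of a case that Table 5 already calls severe. No sample size, power or alpha figure changes.

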6.1.2. Part 2 Halting Rules

- 1. Any participant experiences a vaccine-related SAE.
- 2. Five or more participants experience the same or similar Grade ≥3 solicited AE (first and second vaccinations to be assessed separately).
- 3. Five or more participants experience the same or similar grade ≥3 unsolicited single AE preferred term or clinical laboratory AE which the investigator assesses as possibly, probably or definitely related to study drug administration.
- 4. Occurrence of severe COVID-19 in any participant, per the definition above, and IDMC determines there is evidence of vaccine enhanced COVID-19. If this halting rule is met, all available clinical and preclinical safety and immunogenicity data will be reviewed by

the IDMC to evaluate for potential vaccine enhanced COVID-19.

6.2. Discontinuation of Study Drug

In some instances, it may be necessary for a participant to permanently discontinue study drug (that is, not receive the second vaccination). Please also refer to halting rules described in Section 6.1.

Permanent discontinuation of study drug does not mean withdrawal from the study, and the participant will be encouraged to remain in the study and continue to complete all study visits. At the time of treatment completion or study drug discontinuation, the Early Termination (ET) visit should be completed as shown in the SoA (Section 1.2). Participants should continue to be followed for safety, immunogenicity and efficacy even if they discontinue study drug prematurely unless they withdraw consent.

Participants may discontinue or be discontinued from study drug at any time. A participant may discontinue study drug for reasons including but not limited to:

- Adverse event
- Death
- Lost to follow-up
- Physician decision
- Pregnancy
- Protocol deviation
- Study terminated by Sponsor
- Withdrawal by participant* (*only for discontinuing study drug, but will remain in study)

The reason for participant discontinuation from study drug will be recorded in the eCRF.

6.3. Participant Withdrawal from the Study

Participants have the right to withdraw from the study at any time and for any reason without prejudice to their future medical care by the Investigator or at the institution. A participant may withdraw from the study for reasons including but not limited to:

- Death
- Withdrawal by participant
- Lost to follow-up
- Study terminated by Sponsor

The reason for participant withdrawal from the study will be recorded in the eCRF.

At the time of withdrawal from the study, the ET visit should be completed, as shown in the SoA (Section 1.2).

If the participant withdraws consent for disclosure of future information, the Sponsor may retain and continue to use any data collected before such a withdrawal of consent.

If a participant withdraws from the study, he/she may request destruction of any samples taken and not tested, and the Investigator must document this in the site study records.

6.4. Lost to Follow-up

A participant will be considered lost to follow-up if he or she repeatedly fails to return for scheduled visits and is unable to be contacted by the study site.

The following actions must be taken if a participant fails to return to the clinic for a required study visit:

- The site must attempt to contact the participant and reschedule the missed visit as soon as possible and counsel the participant on the importance of maintaining the assigned visit schedule and ascertain whether or not the participant wishes to and/or should continue in the study.
- Before a participant is deemed lost to follow-up, the investigator or designee must make every effort to regain contact with the participant (where possible, telephone calls and, if necessary, a certified letter to the participant's last known mailing address or local equivalent methods). These contact attempts should be documented in the participant's medical record.
- Should the participant continue to be unreachable, he/she will be considered to have withdrawn from the study.

7. STUDY ASSESSMENTS AND PROCEDURES

- Study procedures and their timing are summarized in the SoA. Protocol waivers or exemptions are not allowed.
- Immediate safety concerns should be discussed with the sponsor immediately upon occurrence or awareness to determine if the participant should continue or discontinue study intervention.
- Adherence to the study design requirements, including those specified in the SoA, (Section 1.2) is essential and required for study conduct.
- All screening evaluations must be completed and reviewed to confirm that potential participants meet all eligibility criteria. The investigator will maintain a screening log to record details of all participants screened and to confirm eligibility or record reasons for screening failure, as applicable.
- Participants who experience any serious or severe TEAEs, MAAEs or experience any event of concern including symptoms of, or a potential exposure to, SARS-CoV-2 should be instructed to contact the study site and be scheduled for a visit for further evaluation. If an unscheduled visit occurs, the reason for the visit and data collected during the visit should be recorded and entered into the unscheduled eCRF.

7.1. Efficacy and Immunogenicity Assessments

Planned time points for efficacy assessments are provided in the SoA in Section 1.2.

7.1.1. SARS-CoV-2 Infection and COVID-19 Diagnosis

Participants will be monitored for SARS-CoV-2 infection and/or symptomatic COVID-19 in the following manner:

- Testing for prior exposure by rapid antibody (Ab) test at Screening and Baseline (prevaccination) if Screening test >7 days prior to Baseline Visit (**Part 1 Cohort 1 only**).
- Testing by an FDA authorized rapid molecular test at any time a participant reports illness compatible with COVID-19 or reports known/ possible exposure to COVID-19. A sample will also be collected at Baseline to test for potential of pre-dose exposure should confirmation of negative infection be needed in participants who contract COVID-19 during the study.
- A negative onsite rapid molecular test is required prior to dosing at Days 1 and 29. This testing is needed given the high rates of COVID-19 being observed at clinical sites with the spread of Omicron variant.

Any participant reporting COVID-19 like illness or exposure to COVID-19 during the study will be asked to return to the site for an unscheduled visit to test for SARS-CoV-2 infection. Any FDA authorized rapid molecular test (e.g. LUCIRA COVID-19 Test) may be used for home or on-site testing for monitoring COVID-19 infection.. Participants with confirmed SARS-CoV-2 infection at any time during the study period will be asked to provide a nasal sample for rapid molecular test every two days after their confirmatory test until they test negative. The duration of q2day testing should end after 10 days if still testing positive at that time. They will also be monitored for clinical disease duration, severity, and outcome. The participant will be counseled

to notify their Primary Care Physician of their positive SARS-CoV-2 status and seek medical care should they become symptomatic.

The occurrence of virologically confirmed (by polymerase chain reaction [PCR] or rapid molecular test to SARS-CoV-2) symptomatic mild, moderate, or severe COVID-19 is defined in Table 5.

Subjects with confirmed COVID-19 will be evaluated for severity of disease as well as for the potential for vaccine-associated enhanced disease (VAED).

Mild	 At least one or more of the following: Fever (defined by subjective or objective measure, regardless of use of anti-pyretic medications)
wind	 New onset cough ≥ 2 COVID-19 respiratory/non-respiratory symptoms in Table 6 AND Does not meet criteria for moderate or severe disease
Moderate	 At least one or more of the following: Fever (defined by subjective or objective measure, regardless of use of anti-pyretic medications) + any 2 COVID-19 symptoms in Table 6 for ≥ 3 days (need not be contiguous days) High fever (≥ 38.4°C) for ≥ 3 days (need not be contiguous days) Any evidence of significant LRTI: Shortness of breath (or breathlessness or difficulty breathing) with or without exertion (greater than baseline) Tachypnea: 20 to 29 breaths per minute at rest SpO2: 94% to 95% on room air Abnormal chest x-ray or chest CT consistent with pneumonia or LRTI Adventitious sounds on lung auscultation (e.g., crackles/rales, wheeze, rhonchi, pleural rub, stridor)
Severe	 At least one or more of the following: Tachypnea: ≥ 30 breaths per minute at rest Resting heart rate ≥ 125 beats per minute SpO₂: ≤ 93% on room air or PAO₂/FiO₂ < 300 High flow oxygen therapy or NIV/NIPPV (e.g., CPAP or BiPAP) Mechanical ventilation or ECMO One or more major organ system dysfunction or failure (e.g., cardiac/circulatory, pulmonary, renal, hepatic, and/or neurological, to be defined by diagnostic testing/clinical syndrome/interventions), including any of the following: ARDS Acute renal failure Acute right or left heart failure Septic or cardiogenic shock (with shock defined as SBP < 90 mm Hg OR DBP < 60 mm Hg Acute stroke (ischemic or hemorrhagic)

Table 5Definitions of COVID-19 Severity

Abbreviations: AMI = acute myocardial infarction; ARDS = acute respiratory distress syndrome; BIPAP = bi-level positive airway pressure; CPAP = continuous positive air pressure; CT = computed tomography; DBP = diastolic blood pressure; DVT = deep vein thrombosis; ECMO = extracorporeal membrane oxygenation; FiO_2 = fraction of inspired oxygen; ICU = intensive care unit; LRTI = lower respiratory tract infection; NIV = non-invasive ventilation; NIPPV = non-invasive positive pressure ventilation; PAO₂ = partial pressure of oxygen in the alveolus; PE = pulmonary embolism; SBP = systolic blood pressure; SpO₂ = oxygen saturation.

Table 6Qualifying Symptoms of Suspected COVID-19

- Fever
- New onset cough
- New onset or worsening of shortness of breath or difficulty breathing compared to baseline
- New onset fatigue
- New onset generalised muscle or body aches
- New onset headache lasting \geq 48 hours
- New loss of taste or smell
- Acute onset of sore throat, congestion, and runny nose
- New onset nausea, vomiting, or diarrhea lasting \geq 48 hours

